10.2 SPEEDLOCK HIP SUTURE ANCHOR

The SpeedLock Knotless Fixation Device is an implant that facilitates the attachment of tissue to bone. The SpeedLock system consists of a fixation device pre-loaded with a suture snare in an inserter handle. The SpeedLock implant is a knotless fixation device, in other words surgical knots are not necessary for fixation of suture to tissue.

10.3 INDICATIONS

The Smith & Nephew PEEK anchors are intended to be used for soft tissue to bone fixation in the hip following hip capsule repair.

Table 3: Part Numbers

Peek Suture Anchors for the Hip

**Part numbers as of September 2018*

Bioraptor Knotless Suture Anchor	72202397
SpeedLock Hip Suture Anchor	OM-7500

CONFIDENTIAL AND PROPRIETARY

This document contains information that is confidential and proprietary to Smith & Nephew PLC and Smith & Nephew, Inc. and is intended for use only by Smith & Nephew and its manufacturer. It shall not be reproduced or copied in whole or in part, nor shall the contents be disclosed by any means without prior written permission from Smith & Nephew, nor shall anyone make any use of it that is contrary to the expressed or implied wishes of Smith & Nephew.

Study Protocol—Device	
PMCF Study on PEEK Suture Anchors for Hip Indications	Number: 2018.14.SMD.PEEK.RET.HIP
	Version: 2.0, 03 April 2019
	Page: 33 of 63

10.4 PRODUCT USE

All study related procedures using the PEEK suture anchors in the hip have been performed according to the recommended surgical technique described in the labelling and the instructions for use.

11. SUBJECT ENROLLMENT AND WITHDRAWAL

Investigators will screen all subjects that have undergone usage of the PEEK suture anchors in the hip using only the existing information in the medical records.

Investigators will conduct a chart review after IRB approval has been granted. All subjects whose chart undergoes the screening process will be documented on a Screening and Enrollment Log, with the reason for exclusion noted, if applicable. The Investigator or designee must notify the Sponsor upon subject enrollment.

11.1 SUBJECT POPULATION

To minimize the potential for selection bias, Investigators will screen and subsequently enroll subjects (after fulfilling all inclusion and exclusion criteria) on whom PEEK suture anchors in the hip were implanted. Enrollment will be in sequential order based on the date of their surgical procedure with the investigational device, i.e. time of surgery to present day.

11.2 INCLUSION CRITERIA

Subjects will be considered qualified for enrollment if they meet the following criteria:

1. Subjects who have undergone hip joint repair using the study devices.
2. Subjects aged 18 years and older at the time of surgery.

CONFIDENTIAL AND PROPRIETARY

This document contains information that is confidential and proprietary to Smith & Nephew PLC and Smith & Nephew, Inc. and is intended for use only by Smith & Nephew and its manufacturer. It shall not be reproduced or copied in whole or in part, nor shall the contents be disclosed by any means without prior written permission from Smith & Nephew, nor shall anyone make any use of it that is contrary to the expressed or implied wishes of Smith & Nephew.

Study Protocol—Device	
PMCF Study on PEEK Suture Anchors for Hip Indications	Number: 2018.14.SMD.PEEK.RET.HIP
	Version: 2.0, 03 April 2019
	Page: 34 of 63

3. Subjects must have had a visit to their provider between 3 and 15 months post-operative.

11.3 EXCLUSION CRITERIA

Any one (1) of the following criteria will disqualify a potential subject from participation in the study:

1. Subjects who are < 12 months post-operative.
2. Subject is entered in another investigational drug, biologic, or device study or has been treated with an investigational product within 30 days prior to surgery.
3. Subject had off-label use of the PEEK suture anchor during surgery.

11.4 SCREENING

Participating study sites are required to document all screened subjects considered for inclusion in this study. If a subject is excluded from the study, the reasons for exclusion will be documented in the subject's source documents and noted on the Screening and Enrollment Log.

11.5 INFORMED CONSENT

For adults and children, a waiver or alteration of the requirements for obtaining informed consent can occur under any of the following three provisions set forth by HHS:

Research in general: an IRB may waive or alter the requirement of informed consent under 45 CFR 46.116(d), provided that the IRB finds and documents that all of the following four conditions are met: [3]

1. the research involves no more than minimal risk to the participants;
2. the waiver or alteration will not adversely affect the rights and welfare of the participants;

CONFIDENTIAL AND PROPRIETARY

This document contains information that is confidential and proprietary to Smith & Nephew PLC and Smith & Nephew, Inc. and is intended for use only by Smith & Nephew and its manufacturer. It shall not be reproduced or copied in whole or in part, nor shall the contents be disclosed by any means without prior written permission from Smith & Nephew, nor shall anyone make any use of it that is contrary to the expressed or implied wishes of Smith & Nephew.

Study Protocol—Device	
PMCF Study on PEEK Suture Anchors for Hip Indications	Number: 2018.14.SMD.PEEK.RET.HIP
	Version: 2.0, 03 April 2019
	Page: 35 of 63

3. the research could not practicably be carried out without the waiver or alteration; and
4. whenever appropriate, the participants will be provided with additional pertinent information after participation.

11.6 ENROLLMENT

Enrollment in this study shall occur when subjects have meet inclusion criteria and none of the exclusion criteria. When a subject is enrolled for the left hip as well as the right hip, only one subject ID will be allocated.

11.7 LOST TO FOLLOW-UP

Not applicable.

11.8 WITHDRAWAL

11.8.1 Withdrawal from the Study

The Investigator may withdraw subjects from the study for many reasons, including but not limited to the following:

- At the discretion of the Investigator.
- If the Investigator or the Sponsor stops the study for any reason and decides to withdraw subject(s) from the study.

For each case, information will be documented in the source document and the Case Report Form (CRF), detailing circumstances leading to the withdrawal.

Subjects who are withdrawn will not be re-entered into the study at a later date. Data collected up to the point of withdrawal may be used but no additional data for that subject may be collected.

CONFIDENTIAL AND PROPRIETARY

This document contains information that is confidential and proprietary to Smith & Nephew PLC and Smith & Nephew, Inc. and is intended for use only by Smith & Nephew and its manufacturer. It shall not be reproduced or copied in whole or in part, nor shall the contents be disclosed by any means without prior written permission from Smith & Nephew, nor shall anyone make any use of it that is contrary to the expressed or implied wishes of Smith & Nephew.

Study Protocol—Device	
PMCF Study on PEEK Suture Anchors for Hip Indications	Number: 2018.14.SMD.PEEK.RET.HIP
	Version: 2.0, 03 April 2019
	Page: 36 of 63

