12.2 ALLOCATION AND BLINDING

This study is not randomized or blinded.

CONFIDENTIAL AND PROPRIETARY

This document contains information that is confidential and proprietary to Smith & Nephew PLC and Smith & Nephew, Inc. and is intended for use only by Smith & Nephew and its manufacturer. It shall not be reproduced or copied in whole or in part, nor shall the contents be disclosed by any means without prior written permission from Smith & Nephew, nor shall anyone make any use of it that is contrary to the expressed or implied wishes of Smith & Nephew.

Study Protocol—Device	
PMCF Study on PEEK Suture Anchors for Hip Indications	Number: 2018.14.SMD.PEEK.RET.HIP
	Version: 2.0, 03 April 2019
	Page: 37 of 63

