12.3 STUDY ENDPOINTS

12.3.1 Primary Endpoint

The primary endpoint will be clinical success rate (%) at 6 months post-operative based on standard of care. Clinical success is defined as hip repairs without signs of device failure and/or re-intervention as assessed by the surgeon.

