This document contains information that is confidential and proprietary to Smith & Nephew PLC and Smith & Nephew, Inc. and is intended for use only by Smith & Nephew and its manufacturer. It shall not be reproduced or copied in whole or in part, nor shall the contents be disclosed by any means without prior written permission from Smith & Nephew, nor shall anyone make any use of it that is contrary to the expressed or implied wishes of Smith & Nephew.

Study Protocol—Device	
PMCF Study on PEEK Suture Anchors for Hip Indications	Number: 2018.14.SMD.PEEK.RET.HIP
	Version: 2.0, 03 April 2019
	Page: 63 of 63

- i. make all reasonable efforts to ascertain the reason(s) for a subject's premature withdrawal from the clinical investigation while fully respecting the subject's rights.

8. Safety reporting. The Principal Investigator shall:

- a. record every adverse event and observed device deficiency, together with an assessment,
- b. report to the Sponsor, without unjustified delay, all serious adverse events and device deficiencies that could have led to a serious adverse device effect; this information shall be promptly followed by detailed written reports, as specified in the protocol,
- c. report to the IEC serious adverse events and device deficiencies that could have led to a serious adverse device effect, if required by the national regulations or protocol or by the IEC,
- d. report to regulatory authorities serious adverse events and device deficiencies that could have led to a serious adverse device effect, as required by the national regulations, and
- e. supply the Sponsor, upon Sponsor's request, with any additional information related to the safety reporting of a particular event.

CONFIDENTIAL AND PROPRIETARY

This document contains information that is confidential and proprietary to Smith & Nephew PLC and Smith & Nephew, Inc. and is intended for use only by Smith & Nephew and its manufacturer. It shall not be reproduced or copied in whole or in part, nor shall the contents be disclosed by any means without prior written permission from Smith & Nephew, nor shall anyone make any use of it that is contrary to the expressed or implied wishes of Smith & Nephew.

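### Section 11.8.1 lets an investigator who can already read the outcome withdraw an enrolled subject, and does not require that subject's outcome to be collected or used

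*Combined protocol and SAP*

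**What the plan says.** Section 11.8.1 opens with an open-ended list: "The Investigator may withdraw subjects from the study for many reasons, including but not limited to the following". The first listed ground is "At the discretion of the Investigator". The second applies when the study is stopped. For each withdrawal the source document and CRF must carry a record "detailing circumstances leading to the withdrawal". On the data themselves the section says: "Data collected up to the point of withdrawal may be used but no additional data for that subject may be collected".

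The setting is retrospective. Section 11 has charts screened "using only the existing information in the medical records", and section 11.3 excludes anyone less than 12 months post-operative. Section 12.2 states: "This study is not randomized or blinded". Section 12.3.1 sets the primary endpoint: "Clinical success is defined as hip repairs without signs of device failure and/or re-intervention as assessed by the surgeon".

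Section 14.2 defines the safety population (SAF) as all enrolled subjects who had the hip repair. The per-protocol population (PP) is the part of SAF that is eligible and free of significant deviations. Section 14.3.1 makes PP primary for the 6-month rate and SAF the sensitivity set. Sections 14.3.2, 14.4 and 14.5 use SAF. Neither definition mentions withdrawn subjects, and section 11.7 (lost to follow-up) is marked not applicable.

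**The concern.** Discretionary withdrawal makes sense in a prospective trial, where it can take a patient off a study treatment or a burdensome schedule. Here surgery and follow-up are already over or nearly so, and all the study does is read the chart. Withdrawal protects the subject from nothing except being counted.

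The person who may withdraw the subject can also normally see whether the repair failed. Section 11.1 relies on sequential enrolment to limit selection bias, but that control acts only up to enrolment. A later exclusion that may depend on the outcome reopens the same bias. Its expected direction is favourable: a higher success rate and lower device-failure and re-intervention rates. The exact confidence interval reflects sampling error only and would not show it.

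**Working it through.** **Is the outcome visible when withdrawal is decided?** The Schedule of Events sets the 6-month review at 182 ± 91 days, so the window closes at 182 + 91 = 273 days. Exclusion criterion 1 requires at least 12 months since surgery, about 365 days. The 6-month window has therefore closed for every subject before enrolment. The 12-month window closes at 365 + 91 = 456 days, so it may still be open for some. I say normally visible, not always, because the visit required by inclusion criterion 3 need not fall inside the 6-month window.

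**Is there a gap between enrolment and data entry?** Under 11.6 enrolment occurs once the criteria are met. In 13.1, implant status and adverse events come later in the list than eligibility screening. A failure can therefore be seen after enrolment and before it is on the CRF. Withdrawal at that moment triggers the bar on further collection.

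**Which analyses can lose the failure?**
- Withdrawn before CRF entry: no outcome exists in PP or SAF, and no rule says how a missing outcome counts.
- Withdrawn after CRF entry: the outcome exists, but its use is optional in both sets.
- Withdrawn after CRF entry and data used: the failure still counts in SAF. Withdrawal is not a listed ground for leaving PP, but nothing says the subject stays there.

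**The plan's own figure.** Section 15 gives a probability of 15.2% (n = 20) to 95% (n = 120) for a 95% CI within 80–100% at a true rate of 91%. With the two-sided Clopper-Pearson interval of 14.3.1, n = 20 needs 20/20, because the lower limit for 19/20 is 75.1%. The probability is 0.91^20 = 15.2%, which reproduces. At n = 120 the requirement is 105/120 and the probability is 92.7%; a one-sided 95% limit gives 95.9%. The present point does not depend on these figures.

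**Effect of withdrawing failures.** Inputs: n enrolled, x successes near the planned 91%, and k failures withdrawn with their data lost. The value of k is my assumption, and I take one hip per subject.
- Rate: x/(n − k). Rise in rate: xk / [n(n − k)].
- 95% limits: lower = Beta quantile 0.025 with parameters (x, n − k − x + 1); upper = Beta quantile 0.975 with (x + 1, n − k − x). The upper limit is 100% when x = n − k.

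| n | x | k | Rate | 95% CI |
|---|---|---|---|---|
| 20 | 18 | 0 | 90.0% | 68.3–98.8 |
| 20 | 18 | 1 | 94.7% | 74.0–99.9 |
| 20 | 18 | 2 | 100% | 81.5–100 |
| 40 | 36 | 0 | 90.0% | 76.3–97.2 |
| 40 | 36 | 2 | 94.7% | 82.3–99.4 |
| 120 | 109 | 0 | 90.8% | 84.2–95.3 |
| 120 | 109 | 2 | 92.4% | 86.0–96.5 |

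For k = 2 the rise is 18×2/(20×18) = 10.0 points at n = 20, 36×2/(40×38) = 4.7 points at n = 40, and 109×2/(120×118) = 1.5 points at n = 120.

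**The case against.** The best defence is that SAF already contains every enrolled subject, and withdrawal comes after enrolment. PP excludes only for ineligibility or significant deviations. On that reading nobody leaves a denominator. Withdrawals are also traceable: the circumstances go into the source and CRF, the sponsor is notified of each enrolment, a screening and enrolment log is kept, and monitors check that data are complete (section 18). A separate SAP is promised before database lock (section 14) and could set a rule.

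Much of this stands. The text permits loss of an outcome; it does not direct it, and a reader of the study report could learn how many subjects were withdrawn and why. But traceability is not inclusion: none of these provisions requires the outcome to be abstracted or used. A later SAP could not recover data that the protocol forbids collecting.

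Some stronger readings are tempting and should not be drawn:
- That the sponsor may remove individual subjects at will. The clause applies only when the study is stopped.
- That omitting a subject-initiated reason is a defect. The list is expressly open, and consent may be waived.
- That the bar on further data contradicts 16.2 and item 8e of 26.1, under which the investigator must "supply the Sponsor, upon Sponsor's request, with any additional information related to the safety reporting of a particular event". Those provisions concern supplementary safety documentation, and the two can coexist.

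**Conclusion.** The point holds as a gap in the rules. Section 11.8.1 permits outcome-dependent exclusion after enrolment, and nothing else in the protocol closes it. PP, the primary set, is exposed. SAF is exposed when withdrawal precedes CRF entry or the collected data are not used.

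Two withdrawn failures would raise the rate by 10.0 points at the 20-subject minimum for one anchor, 4.7 points at the overall minimum of 40, and 1.5 points at 120. These figures assume that only failures are withdrawn and that their outcomes are lost, which is the unfavourable extreme. The documents give no number of withdrawals.

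A reader might take a lower limit moving past 80% as turning a failed study into a successful one. Section 15 gives 80–100% as a precision target and says the study is not powered for hypothesis testing, so no decision turns on 80%. Nor do the documents show that such withdrawals occurred or were intended. The change is worth making because it is cheap and the affected rates are what the study exists to report.

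**What to change.** In 11.8.1:
- Delete withdrawal of individual subjects at the investigator's discretion. Limit it to revoked consent, where consent was obtained.
- Make use of data collected before withdrawal mandatory instead of optional.
- Keep subjects found ineligible after enrolment in SAF, with the date and reason logged.
- If the study or a site stops, complete abstraction for subjects already enrolled where the charts remain accessible. This may not be feasible after an investigator departs or a site is closed for non-compliance (section 22).

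In 14.2, state that withdrawn subjects stay in SAF and in the SAF success-rate denominator with chart-derived status, and report their number, reasons and implant status. Where revoked consent leaves no outcome on the CRF, report it as missing and add a sensitivity analysis counting missing outcomes as failures.

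The cost is a few sentences in an amendment. No new procedures are needed because the charts already exist. The reported success rate may be slightly less favourable.

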12. STUDY DESIGN

12.1 STUDY DESIGN

This is a retrospective, open-label, multi-center study to collect clinical data that will evaluate post-market safety and performance of the PEEK suture anchors in the hip. A minimum of 40 subjects and a maximum of 240 subjects in the United States who underwent surgery in the hip using the Smith & Nephew PEEK suture anchors are planned to be enrolled into the study after the fulfilment of all inclusion and exclusion criteria. Up to three sites will enroll a minimum of 20 subjects and a maximum of 40 subjects per anchor configuration; therefore, not more than 120 subjects will be enrolled for any anchor type.

Data obtained from enrolled eligible subjects will subsequently be recorded on case report forms.

Table 4: Enrollment

PEEK Anchor	Minimum Number of Subjects/Site	Maximum Number of Subjects/Site	Maximum Number of Subjects for the Study
Bioraptor Knotless Suture Anchor	20 subjects per site	40 per site	120 subjects
SpeedLock Hip	20 subjects per site	40 per site	120 subjects
Total	40 subjects	80 subjects	240 subjects

12.2 ALLOCATION AND BLINDING

This study is not randomized or blinded.

CONFIDENTIAL AND PROPRIETARY

This document contains information that is confidential and proprietary to Smith & Nephew PLC and Smith & Nephew, Inc. and is intended for use only by Smith & Nephew and its manufacturer. It shall not be reproduced or copied in whole or in part, nor shall the contents be disclosed by any means without prior written permission from Smith & Nephew, nor shall anyone make any use of it that is contrary to the expressed or implied wishes of Smith & Nephew.

Study Protocol—Device	
PMCF Study on PEEK Suture Anchors for Hip Indications	Number: 2018.14.SMD.PEEK.RET.HIP
	Version: 2.0, 03 April 2019
	Page: 37 of 63

12.3 STUDY ENDPOINTS

12.3.1 Primary Endpoint

The primary endpoint will be clinical success rate (%) at 6 months post-operative based on standard of care. Clinical success is defined as hip repairs without signs of device failure and/or re-intervention as assessed by the surgeon.

12.3.2 Secondary Endpoints

The secondary endpoint will be clinical success rate (%) at 12 months post-operative based on standard of care. Clinical success has previously been defined. It is expected that per physician's standard of care, 12 month clinical data will be consistently be available.

12.3.3 Safety Endpoints

Safety endpoints will include but not restricted to the following events:

- All adverse events, SAEs and complications occurring from the time of enrollment until study termination or study completion including intra-operative adverse events and complications.
- Device related intervention.
- Device deficiency.

12.3.4 Other Endpoints

Surgeon Reported Outcomes would constitute other endpoints and may include but not restricted to the following:

- Range of Motion (ROM)
 - Flexion
 - Extension

CONFIDENTIAL AND PROPRIETARY

This document contains information that is confidential and proprietary to Smith & Nephew PLC and Smith & Nephew, Inc. and is intended for use only by Smith & Nephew and its manufacturer. It shall not be reproduced or copied in whole or in part, nor shall the contents be disclosed by any means without prior written permission from Smith & Nephew, nor shall anyone make any use of it that is contrary to the expressed or implied wishes of Smith & Nephew.

Study Protocol—Device	
PMCF Study on PEEK Suture Anchors for Hip Indications	Number: 2018.14.SMD.PEEK.RET.HIP
	Version: 2.0, 03 April 2019
	Page: 38 of 63

- Abduction
- Adduction
- External/Internal Rotation
- Pain assessed by VAS

13. STUDY PROCEDURES

13.1 6 MONTHS POST-OP CHART REVIEW

NOTE: Any subject, who meets the inclusion/exclusion criteria, will be assigned a subject number.

1. Subject should undergo the informed consent process and sign the informed consent *only* if a waiver of consent has not been approved by the IRB.
2. Screen the subject's chart for protocol inclusion/exclusion criteria.
3. Obtain demographic information and a medical history.
4. VAS, ROM.
5. Operative Data Collection – review operative case notes.
6. Implant Status / Disposition.
7. Document concomitant medications and/or therapies associated with an AE, SA(D)E
8. Review the subject's chart for AEs, SAEs and Device Deficiencies, including inter-operative. AEs, SAEs and DevDs should be documented from the time of surgery through the study duration.

CONFIDENTIAL AND PROPRIETARY

This document contains information that is confidential and proprietary to Smith & Nephew PLC and Smith & Nephew, Inc. and is intended for use only by Smith & Nephew and its manufacturer. It shall not be reproduced or copied in whole or in part, nor shall the contents be disclosed by any means without prior written permission from Smith & Nephew, nor shall anyone make any use of it that is contrary to the expressed or implied wishes of Smith & Nephew.

Study Protocol—Device	
PMCF Study on PEEK Suture Anchors for Hip Indications	Number: 2018.14.SMD.PEEK.RET.HIP
	Version: 2.0, 03 April 2019
	Page: 39 of 63

13.2 12 MONTHS POST-OP CHART REVIEW

